To maintain the privacy information of study participants, only pertinent research personnel will have access to participant information. Research personnel are employees of CCHMC and have been trained in human participant's research and HIPAA compliance. To further insure privacy, all data will be analyzed and tracked using a coded identification number that does not use identifiable personal information. Personal information and identifiers will be securely recorded and filed by the administrative assistant. The data will be encrypted with a password and stored on a personal computer and backed up on a network drive. The participant identification code will be used on all data questionnaires.

The results of this study will be kept confidential. No participant identification will be made public record in any form unless the participant gives his or her expressed written permission of release of participant's name, photograph or likeness captured on video. The investigators will be available for any questions that may arise.

To further insure confidentiality, only pertinent research personnel will have access to participant information. Research personnel are employees of CCHMC and have been trained in human subjects research and HIPAA compliance.

(16) COST OF PARTICIPATION:

Participants will endure no costs other than time and effort in participating in this study. Insurance will not be billed for any of the tests associated with this study.

(17) PAYMENT FOR PARTICIPATION:

Participants will be compensated for their time and effort in participating in this study. They will receive a \$50 Clincard Mastercard® gift card for completing the testing. Registration in the Clincard payment system requires a social security number, which will be acquired via a complete W-9 form for each participant. Participants will be compensated even if they are not able to complete the entire MRI session.

References Cited

1. Hoge, C.W., et al., *Mild Traumatic Brain Injury in U.S. Soldiers Returning from Iraq*. New England Journal of Medicine, 2008. **358**(5): p. 453-463.
2. Okie, S., *Traumatic brain injury in the war zone*. N Engl J Med, 2005. **352**(20): p. 2043-7.
3. Xydakis, M.S., et al., *Analysis of battlefield head and neck injuries in Iraq and Afghanistan*. Otolaryngol Head Neck Surg, 2005. **133**(4): p. 497-504.

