I. An *in vivo* clinical trial was approved by CCHMC IRB and was completed in the Cincinnati Children's Hospital Human Performance Laboratory and Radiology Department (Study ID: 2015-2205; PI: [name]). We sought to (1) identify brain networks in performance of a cognitive task, (2) evaluate whether longitudinal changes in performance are associated with alterations in brain network connectivity after a season of head contact competitive play, and (3) determine the effect of a jugular vein compression device on these relationships. Male high school football athletes were assigned to a collar (N=12, age=16.4±1.2) or non-collar group (N=13, age=16.2±1.6). Subject response times (RT) during a visual go/no-go test were recorded before and after the season. Neuroimaging data were acquired prospectively pre and post season. Functional networks were parcellated from preseason data via independent component analysis and intersected with the Harvard-Oxford brain atlas to form regions of interest. For all subjects at preseason, RT were positively correlated with connectivity within the salience network (r=0.47, p=0.003) but not any other network (p>0.05). Consequently, we evaluated associations between longitudinal changes in RT and connectivity within this network for each group; changes in RT were positively correlated with changes in connectivity for the non-collar group (r=0.58, p=0.038) but not the collar group (r=0.38, p=0.221). The salience network was associated with RT in a visual go/no-go task, consistent with its central role in motivation and a readiness to act. Associations between altered RT and network connectivity for only the non-collar group suggests not only that

exposure to head impacts may affect critical processing within the salience network, but that the collar may afford a protective effect in stabilizing brain network connectivity.

(4) STUDY DESIGN:

All testing will be performed in the SPORT Center, Division of Sports Medicine at Cincinnati Children's Hospital. Ultrasound testing will consist of measurement of dilation and compression of the jugular veins following the application of a generic jugular vein compression device. The ultrasound testing will be completed in 20 minutes or less.

(5) DURATION:

Each participant will participate in 1 planned study visit that may take up to 20 minutes. Data analysis will continue for a 6 month period following the final enrollment.

(6) SELECTION & RECRUITMENT OF PARTICIPANTS

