Sitting upright, and facing forward, ultra-sound coupling gel is applied to the lateral neck, and the right side common carotid artery, and IJV in the transverse plane, are identified to verify normal anatomy. Collar positions will be marked on the neck using stickers or other temporary marking methods. The collar is then placed into proper position on the study volunteer's neck. To further evaluate responsiveness to the collar, a 15 s video clip is obtained, recording the collar in its proper position, the collar opened away from the neck, and the collar returned to its proper position. The largest transverse dimension at initial collar placement, and the smallest transverse dimension at opened collar view and again at proper collar replacement, will be used for IJV metrics.

IJV Compression ultra-sound imaging

With proper placement of IJV compression collar confirmed, pressure is increased in small intervals of pressure unilaterally until IJV compression is visually observed. The collar will then be rotated radially anterior and posterior to its initial position around the IJV. This process will be repeated at .2 increments of pressure until the 1.5 lbs pressure of the standard collar is achieved. The ultrasound technologist will record the jugular vein measurements relative to each indicated pressure level.

(9) DATA ANALYSIS/METHODS:

Data Storage.

The personal demographic data for each participant will be blinded from the researchers, and a coded identification number will be used to track all collected data. Data will be stored on password-protected computers and only pertinent research personnel will have access. Data forms will be stored by coded identification number in a locked cabinet to which only pertinent research personnel have access. All data will be collected for research purposes only.

Statistical analyses will be performed with SPSS statistical software (SPSS Inc, Chicago IL). Data regarding the descriptive information (such as mean and standard deviation) will be calculated for demographic, anthropometric and ultrasound variables of interest. Sex and age specific analysis will be compared between the test conditions (baseline vs. X pressure) using a paired student T-test.

(10) FACILITIES AND PERFORMANCE SITES:

All ultrasound testing will be performed in the SPORT Center in the Division of Sports Medicine.

(11) POTENTIAL BENEFITS:

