Although the venous jugular flow beneath the pressure cuff may be temporarily halted or slowed, the venous outflow from the cranium is never completely stopped, particularly from the anastomosis between the spinal vein and the basilar plexus and occipital sinuses *which are incompressible.*”(Gregg and Shipley 1944) Jugular compression has few known physiological effects besides the intended increase in cerebral blood volume and pressure. Only one innocuous physiology has ever been shown to alter with jugular compression. “Previous studies have shown that the decline in urinary sodium excretion which occurs normally in the sitting position, as compared with recumbency, can be partially but not completely prevented by compression of the neck (Lewis, Buie et al. 1950, Torres and Ellington 1970). This decline in urinary sodium excretion is minimal. There was no correlation between EEG changes and changes in systolic blood pressure occurring during jugular or carotid compression(Torres and Ellington 1970). Further, studies on complete resection of the IJV note that, “the clinical observation that bilateral resection of the IJV is usually well tolerated suggests the presence of alternative, non-jugular pathways.”(Gius and Grier 1950)

Effect of Body Position and Exercise on ICP: “At rest, compared with the reference 30-degree head-up position, the supine position increased intracranial pressure (ICP) by 6.21 mm Hg (35% with $P < .01$).”(Brimioulle, Moraine et al. 1997) Restated, just lying down increases ICP more than the Device (6.21mm Hg = 35% rise versus this device at only 25%). *Valsalva and raising ICP:* We define Valsalva, where a person tries to exhale forcibly with a closed glottis (windpipe), so that no air goes out through the mouth or nose. “When the Valsalva maneuver was performed during resistance exercise, the ICP rose to 31 mmHg (a rise of 138%). No complications were associated with participating in this investigation.”(Haykowsky, Eves et al. 2003) In other words, the Device facilitates the intended actions of the omohyoid with less pressure than the act of lying down or performing the Valsalva (holding one’s breath and bearing down, which would be expected to occur regularly on a playing field).

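### Breathing is not controlled, and the collar clip compares a largest with a smallest vein dimension, so breathing variation can be read as a collar response

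*Combined protocol and SAP*

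**What the plan says.** The standard-collar part of section (8) fixes the participant's posture and head direction and marks the collar position on the neck. Then "a 15 s video clip is obtained, recording the collar in its proper position, the collar opened away from the neck", and finally the collar put back. How the 15 s divide among the three states is not stated. The read-out rule is "The largest transverse dimension at initial collar placement" together with "the smallest transverse dimension at opened collar view and again at proper collar replacement, will be used for IJV metrics". So state 1 is read as a maximum and state 2 as a minimum. As the sentence is written, state 3 is a minimum too.

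For the pressure steps, section (8) raises the pressure until compression is seen by eye. It rotates the collar forward and backward and repeats in 0.2 increments up to 1.5 lbs. The measurement instruction is: "The ultrasound technologist will record the jugular vein measurements relative to each indicated pressure level". It gives no duration, number of readings or read-out rule.

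No section gives a breathing instruction, a breath phase for reading, or a rule to repeat a recording spoiled by strain. Section (6) requires tolerance of hypercapnia, but no described procedure uses it and it controls nothing here. Section (12) does say that yawning can collapse the jugular veins and that straining against a held breath raises intracranial pressure (ICP). Section (9) plans paired t-tests of baseline against each pressure, by sex and age.

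**The concern.** The protocol itself accepts that breathing manoeuvres affect these veins, yet leaves breathing uncontrolled while the veins are measured. Two kinds of error follow.

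- **Systematic error in the clip.** A maximum over one period is set against a minimum over another. Any variation within a period, including ordinary breathing, widens that difference in one direction. A participant who braces or holds a breath as someone moves the collar would add an error tied to the collar move, and no stated step would detect it.
- **Noise at the pressure steps.** Readings at an arbitrary point of the breath scatter around the true value. Section (3) aims to find the lowest relative pressure that produces a vein response. A breath-related narrowing could be taken for that threshold or could hide it. The sex and age analyses use subsets of about 100 people, so added noise costs more there.

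**Working it through.** The plan gives no SD, effect size, alpha or power, so there is no figure of its own to reproduce.

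**Inputs from the documents:** one 15 s clip; three states; maximum in state 1, minimum in states 2 and 3; about 100 participants, about 50 per sex; ages 7 to 60.

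**Assumptions, not in the documents:** resting rates of 12 to 20 breaths/min in adults and up to 25 in young children; a sinusoidal breathing swing S (peak to trough) of 5% to 20% of vein dimension; a 10% SD of the paired difference from all other sources; two-sided alpha 0.05.

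**Step 1. Time per state.** 15 / 3 = 5.0 s on average. If each of the two collar moves takes 1 s, (15 − 2) / 3 = 4.3 s; if 2 s, (15 − 4) / 3 = 3.7 s.

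**Step 2. Breaths in 5 s** (5 × rate / 60): 1.0 at 12/min, 1.33 at 16/min, 1.67 at 20/min, 2.1 at 25/min. That is about 1 to 2 breaths.

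**Step 3. False difference with no collar effect.** If a state holds a full breath, its maximum is the mean + S/2 and its minimum is the mean − S/2. State 1 minus state 2 is then S/2 − (−S/2) = S, the whole swing. Simulation with random phase gives 100% of S for 5 s states and 97% to 100% for 3.7 s states. The same holds for state 1 against state 3 as written, although the collar is in the same position in both.

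**Step 4. Consequence for a paired t-test of on against open when the collar does nothing** (3,000 simulated trials per row, 5 s states, rates 12 to 20/min):

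| n | S | Rejects, maximum (state 1) vs minimum (state 2) | Rejects, minimum (state 3) vs minimum (state 2) |
|---|---|---|---|
| 10 | 5% | 30.0% | 5.4% |
| 10 | 10% | 82.3% | 5.4% |
| 50 | 5% | 93.1% | 4.5% |
| 50 | 10% | 100% | 4.5% |
| 100 | 5% | 99.9% | 5.1% |
| 100 | 10% | 100% | 5.1% |

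Hand check for n = 50, S = 5%: noncentrality = (0.05 / 0.10) × √50 = 3.54, which agrees with rejection in about 93% of trials. The like-for-like column stays near the nominal 5%.

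**Step 5. Single readings at random phase, as the pressure steps allow.** Each reading has variance (S/2)²/2, so the difference of two has SD S/2 and mean zero (simulated SD 0.50 S). For S of 5% to 20% the added SD is 2.5% to 10% of vein size. This is noise, not bias.

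**The case against.** The best defence is that the clip does have a read-out rule. Where a state holds a full breath, its largest and smallest values do not depend on the breath phase in which recording starts, and random phase averages out across participants. That is correct, and it rules out clip length as the main cause. It does not rescue the contrast, because the rule takes opposite extremes in the states being compared.

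It is also fair that the documents give no breathing effect on vein size, so the rejection rates above are illustrations. Section (9) does not say which clip dimension, if any, serves as baseline in the t-test.

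Several stronger readings are tempting and not supported:

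- **Each state lasts at most 5 s, about one breath.** No split is stated; 5 s is the upper limit of the average only.
- **Breathing outweighs the collar 5.5 times (138% / 25% in section (12)).** Those figures are ICP, not vein dimension, and the 138% comes from Valsalva during resistance exercise. Participants here sit still.
- **100 participants carry the information of only 90 to 50.** That calculation assumes single frames at random phase, which is not how the clip is read.
- **Breathing rate biases the age comparison.** A 2.5 s window gives an 18-point gap in expected peak between 12 and 20 breaths/min. The documents give no reason for that window; the gap falls to 3 points at 3.7 s and to zero at 5 s.

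**Conclusion.** The concern holds in this form: breathing is uncontrolled in the clip and at the pressure steps, and the largest-versus-smallest rule turns breathing variation into apparent collar response. Under a regular breathing pattern the false difference is essentially the full breathing swing, whatever its size. The absence of breathing control and the opposing read-out rules come directly from the text. The breath counts, swing sizes and rejection rates rest on the labelled assumptions. Error from a held breath is possible but cannot be sized from the documents. At the pressure steps the demonstrated harm is added noise and a less certain threshold, not a demonstrated bias. This does not show that the collar response is an artefact. It shows that the clip as specified cannot separate that response from breathing, and that the remedy is cheap enough to adopt.

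**What to change.** 1. Instruct quiet breathing without breath-holding for all recordings.
2. Replace the largest/smallest rule, explicitly, with one identical read-out in every collar state: for example, the dimension at end-expiration averaged over about three consecutive breaths. State how end-expiration is identified.
3. Lengthen each state to hold those breaths. At the slowest assumed rate, three breaths take 3 × 60 / 12 = 15 s. Lengthening without step 2 leaves the bias in place.
4. Repeat any clip with a visible strain or breath-hold.
5. At each pressure level, save a short clip and apply the same read-out.

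Cost: three states of 15 s make 45 s, which is 30 s more than now. For the pressure steps, assume up to 7 levels (1.5 / 0.2 = 7.5) and 3 collar positions: 21 clips × 15 s = 315 s, a little over 5 minutes, plus repeats and added reading time. Staff and machine are unchanged. The total must be checked against section (4): "The ultrasound testing will be completed in 20 minutes or less".

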We aim to recruit approximately 100 healthy volunteers divided equally between the sexes. The normal, healthy participants (age 7-60 years old) will be recruited from local school districts local sports clubs and teams, local colleges, adult sport leagues, and professional sports teams, through our well established network with area coaches and athletic trainers. To obtain the various age groups we will also recruit from that we may recruit from colleagues and staff members. All recruited participants will be made aware that participation is voluntary and will not be held against them if they decide not to participate. Questions regarding participation will be answered during the presentations or through e-mail or phone. Participants will be contacted via telephone to further explain the study, answer any additional questions and to enroll them in the study. The participants and parents/guardians (if subject under age of 18) who voluntarily agree to participate will be scheduled to complete the pre-participation testing. The participant and parent/guardian (if subject under the age of 18) will read and sign the "Consent to Participate in a Research Study" form, approved by the Institutional Review Board of Cincinnati Children's Hospital. If the participant and parent/guardian does not read or sign the form, they will not participate in the study. Additional Adult volunteers will be recruited via word of mouth or through affiliations with the teams/clubs noted above, through personal contacts, or through emails sent via Clinical Studies.

Inclusion criteria

- Normal healthy volunteer aged 7-60
- Able to provide written consent
- Able to tolerate hypercapnia for 1-2 minutes

Exclusion criteria

- Unable to provide written consent
- History of neurological deficits, previous cerebral infarction, or severe head trauma as indicated through pre-season screening:
- Medical contraindications to restriction of venous outflow via the internal jugular veins (known increased intracerebral pressure, metabolic acidosis or alkalosis)
- Glaucoma (Narrow Angle or Normal Tension)
- Hydrocephalus
- Recent penetrating brain trauma (within 6 months)

- Known carotid hypersensitivity
- Known increased intracranial pressure
- Central vein thrombosis
- Any known airway obstruction
- Any known seizure disorder

(7) PROCESS OF OBTAINING CONSENT

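### The standard-collar clip reads its collar-on and open states by opposite extremes and never combines or compares the two collar-on readings

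*Combined protocol and SAP*

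**What the plan says.** In the Combined protocol and SAP, section (8), under the standard-collar baseline imaging heading, the clip is introduced with "To further evaluate responsiveness to the collar, a 15 s video clip is obtained". It has three phases: "recording the collar in its proper position, the collar opened away from the neck, and the collar returned to its proper position". For the first phase the reading is specified as "The largest transverse dimension at initial collar placement". The other two phases are covered by a different rule: "the smallest transverse dimension at opened collar view and again at proper collar replacement, will be used for IJV metrics". No formula follows for turning the three readings into a metric.

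Section (9) has two analysis statements. The first is descriptive: "Data regarding the descriptive information (such as mean and standard deviation) will be calculated for demographic, anthropometric and ultrasound variables of interest". The second is the only test: "Sex and age specific analysis will be compared between the test conditions (baseline vs. X pressure) using a paired student T-test". Baseline is not tied to any one of the three clip readings. No averaging, on-on comparison, drift check or repeatability statistic is named.

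Section (6) gives the sample size: "We aim to recruit approximately 100 healthy volunteers divided equally between the sexes". No SD, effect size or power accompanies it.

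**The concern.** Filming on, off and on again is a good small design. It offers a within-person contrast, a second look at the treated state and protection against drift. Two things in the plan stop it delivering these.

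First, the reading rule changes between states. A vein dimension that fluctuates during the clip has a maximum above its minimum whether or not the collar does anything, so the first on-minus-open difference has a built-in positive component. That component grows with the fluctuation within a phase. If fluctuation differs by age or sex, it could pass for an age or sex difference in response, which is what the study sets out to describe.

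Second, even with a common rule, nothing tells the analyst to average the two collar-on readings or look at their difference. Some precision, the drift protection and the only scheduled repeat of a nominally identical state would go unused.

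**Working it through.** The plan states no figure on this point, so there is nothing to reproduce. The inputs from the documents are the three phases, the largest/smallest rule and about 100 participants. All variances below are assumed.

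**1. Effect of the reading rule.** Suppose the collar has no effect and each phase yields m independent normal frames with the same mean and SD (200,000 simulated draws). Results are in units of one frame's SD.

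| m | first on (max) − open (min) | mean of on (max) and on (min) − open (min) | SD from on-on pairs, √(Σd²/2n) | true SD of one extreme |
|---|---|---|---|---|
| 2 | 1.12 | 0.56 | 1.14 | 0.82 |
| 5 | 2.33 | 1.16 | 1.78 | 0.67 |
| 20 | 3.73 | 1.87 | 2.69 | 0.52 |

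The correct value in the two contrast columns is 0. Averaging the readings as written only halves the artefact, and the simple repeatability formula overstates the error. On the literal text, the second on-minus-open difference is minimum against minimum and carries no such bias. If the sentence instead means that the largest dimension is taken again at replacement, the two collar-on readings match. Both are then compared with an open-state minimum, and the bias in the first contrast column applies to each.

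**2. Precision from averaging, once one rule applies.** Let w be the variance of a single reading, b the between-person variance of the true response, and r = b/w.

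- One on-reading minus open: variance b + 2w.
- Mean of two on-readings minus open: variance b + w/2 + w = b + 1.5w.
- Ratio of standard errors: √((r + 1.5)/(r + 2)).

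| r | SE ratio | SE reduction | 100 participants then equal |
|---|---|---|---|
| 0 | √(1.5/2) = 0.866 | 13.4% | 133 |
| 1 | √(2.5/3) = 0.913 | 8.7% | 120 |
| 2 | √(3.5/4) = 0.935 | 6.5% | 114 |
| 4 | √(5.5/6) = 0.957 | 4.3% | 109 |
| 9 | √(10.5/11) = 0.977 | 2.3% | 105 |

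**3. Drift.** Let the true response be D and let the reading drift by c per phase, with phases equally spaced. The three readings are D, c and D + 2c. Then on1 − open = D − c, on2 − open = D + c, and their mean is D. The section gives no phase durations, so equal spacing is an assumption.

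**4. Repeatability.** With d = on1 − on2, the within-person SD is SD(d)/√2, taking the SD about the mean of d. Drift makes the mean of d equal to −2c, and √(Σd²/2n) would count that shift as reading error. The chi-square 95% limits for the SD are about 0.88 to 1.16 times the estimate from 100 pairs, and 0.84 to 1.24 times from 50 (one sex). Removing the mean costs one degree of freedom and changes these very little.

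**The case against.** The strongest reply is that the plan is silent rather than wrong. All three readings are assigned to the IJV metrics, so a reader who infers that the second collar-on reading is thrown away goes further than the text. Averaging is unstated, not ruled out. That stands. The opposite-extremes rule, however, is stated.

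It can also be said that the clip is secondary. The only test is "compared between the test conditions (baseline vs. X pressure) using a paired student T-test", baseline is undefined, and if it means the open state, averaging the collar-on readings does nothing for the pressure steps. Precision for the standard-collar effect is not evidently short either: item F of section (3) reports IJV dilation at p < .01 in a trial with 31 collar wearers. Both points stand and limit the gain.

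A reader might infer that the paired test is invalid without a repeatability estimate. It is not, because the SD of the paired differences already contains reading error.

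A reader might also want to turn the on-on SD into a cut-off below which no single vein's change at any pressure step counts as a response. The documents do not support this. The on-on difference reflects immediate re-application of the standard collar within one clip. The steps involve unilateral incremental pressure with the collar rotated, and nothing shows that the error is the same. The plan also has no numeric per-vein response rule: compression is judged by eye and inference is at group level.

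**Conclusion.** The point holds in a limited form. As written, the two collar-on readings are not replicates, and the first on-minus-open contrast is inflated in the absence of any response. The simulated 1.1 to 3.7 frame-SDs assumes 2 to 20 independent normal frames per phase; the direction does not depend on those choices, but the size does. This is the more important half, because it is a bias and not a loss of precision.

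The gain from averaging is real but modest: 13% of the standard error at most, about 9% when between-person and reading variances are equal, and 4% to 2% at ratios of 4 to 9. The upper figure, equivalent to a third more participants, needs everyone to have the same true response. That is hard to credit across ages 7 to 60 and both sexes, so it should not be quoted alone. The gain belongs to the standard-collar contrast. It reaches the planned t-test only if baseline is the collar-on clip reading. The repeatability figure would cover immediate re-application only, not reader or session variation.

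**What to change.** In section (8), read all three phases by one rule. The phase mean is the simplest choice. If an extreme is kept, use the same one in every phase over windows of equal length, because the expected extreme grows with the number of frames.

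In section (9):

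- Define the standard-collar response as the mean of the two collar-on readings minus the open reading.
- State which clip reading, if any, serves as baseline in the paired t-test.
- Report the mean on1 − on2 difference and the within-person SD with that mean shift removed, labelled as descriptive repeatability of immediate re-application.
- Do not use that SD as a single-vein response threshold at the pressure steps.

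The cost is a few sentences of text and some reading time on video that is already to be recorded. No participant, visit or procedure is added.
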